9.4.2 Safety Analyses

Safety analysis will be based on the safety set.

Adverse events will be analyzed using quantitative and qualitative measures. Treatment-emergent adverse events will be summarized by treatment group for all AEs, related AEs, serious adverse events, deaths, adverse events leading to discontinuation of blinded study medication or to withdrawal from study, adverse events of different severity and adverse events of different chronicity. Treatment-emergent adverse events will be coded using the Medical Dictionary for Regulatory Activities (MedDRA) and summarized by system organ class and preferred term for each treatment group. For selected adverse events, time to first event will be visualized using Kaplan-Meier plots.

Laboratory data will be summarized by each visit including change from baseline. The number of normal, abnormal not clinically significant and abnormal clinically significant values on each parameter will be summarized for change over study using shift tables. All data will be listed and values outside reference ranges will be highlighted in the listings.

Vital signs and continuous parameters from the ECGs will be summarized by each visit including change from baseline. Values outside pre-specified ranges (low, high) or changes exceeding pre-specified limits will be summarized by visit for each parameter. The number of normal, abnormal not clinically significant and abnormal clinically significant values on the ECG overall evaluation will be summarized for change over study using shift tables. All data will be listed and values outside reference ranges will be highlighted in the listings.

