7.2 Study Participation After Discontinuation of Blinded Study Medication

Patients may permanently discontinue blinded study medication before the end of the study if they choose to or at the investigator's discretion.

Patients who permanently discontinue blinded study medication are not required to withdraw from the study unless they test positive for COVID-19 active disease. Patients who have permanently discontinued blinded study medication but do not test positive for COVID-19 active disease and have not withdrawn consent may continue in the study and complete all remaining protocol specified visits.

The Investigator must document the reason for discontinuation of blinded study medication in the eCRF.

Ideally, patients who have permanently discontinued blinded study medication will continue to attend scheduled clinic visits and complete important efficacy and safety assessments. However, if this is not possible then the investigator will encourage the patient to select one of the three options below to participate in as much of the study as they are willing (or able) to participate:

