7.3.1 Early Termination/Withdrawal Procedures

If a patient is withdrawn prior to the Week 12 visit, every attempt should be made to have the patient complete the early termination/ withdrawal procedures in the SoA (Section 1.3) as soon as possible.

- If possible, patients should remain on blinded study medication and their maintenance LAMA or LABA medication and ICS (if applicable), follow the withholding procedures prior to Spirometry in Section 8.3.1.2, and should refrain from smoking or caffeinated beverages as recommended in Section 5.4.1.1.
- Patients unable to remain on blinded study medication and/or their maintenance LAMA or LABA medications and ICS (if applicable) should still complete the early termination/ withdrawal visit as soon as possible.

7.3.1.1 12-Hour Spirometry and 1.5 Hour ECG Procedures

For patients who are withdrawn prior to completing the Week 12 visit only, every attempt should be made to have the patient complete the 12-hour spirometry procedures and the ECG procedures at the early termination/withdrawal visit unless consent is withdrawn or the patient is being withdrawn for safety reasons precluding this assessment.

Patients who Continued Blinded Study Medication

Patients who have continued administration of their blinded study medication should complete the spirometry and ECG procedures as follows:

- Spirometry: Pre-dose and 0-12-hour post-dose assessments as per Section 1.4 and Section 8.3.1.
- ECG: Pre-dose and 1.5-hour post-dose ECG procedures as per Section 8.4.2.

Patients who Discontinued Blinded Study Medication

Patients who have discontinued blinded study medication prior to the early termination/withdrawal visit may optionally complete spirometry and ECG assessments at the early termination visit if they have not already completed the Week 12 assessments. These patients will not be dosed with blinded study medication. If possible, patients should start spirometry between 6 am and 10am, withhold rescue medication and/or maintenance LAMA or LABA medications for the time period specified in Section 6.7.2, and refrain from caffeinated beverages and/or smoking for the time period specified in Section 5.4.1. The spirometry and ECG procedures should be completed as follows:

- Spirometry: Serial spirometry at 0-hour, 30 min, and 1, 2, 4, 6, 8, and 12 hours.
- ECG: 12-lead ECG at 0-hour and 1.5 hours.

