9.2 Sample Size Determination

Approximately 800 patients will be randomized. The standard deviation for the change in FEV₁ AUC_{0-12h} is estimated to be 250 mL. With a 2-sided test at a 5% significance level and 500 vs. 300 evaluable patients in the two groups, there will be an 90% power to detect a true difference of 59 mL between the treatments. If the withdrawal rate at 24 weeks exceeds 25% overall, additional patients may be randomized to the study to compensate for the loss of data.

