6.3. RETESTS, UNSCHEDULED VISITS AND EARLY TERMINATION DATA

In general, for by-visit summaries, data recorded at the nominal visit will be presented.

Patients who were a screen failure and received approval from the Medical Monitor for rescreening will go through all of the original screening assessments. Data from the latest rescreened visit will be used in the summaries, however all screening information will be listed. Rescreened patients will keep the same patient number, as for the initial screening. Unscheduled measurements will not be included in by-visit summaries but will contribute to the EOS value, or best/ worst case value where required (e.g. shift table).

Early termination data will be mapped to the next available visit number for by-visit summaries, as described in section 6.4 of the SAP.

Post-randomization if ECG result is Abnormal, Clinically Significant, then triplicate ECGs should be provided.

Listings will include scheduled, unscheduled, retest and early discontinuation data.

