17.1. ADVERSE EVENTS

Adverse Events (AEs) will be coded using MedDRA central coding dictionary. The version of MedDRA to be used will be specified prior to database lock.

Treatment-emergent adverse events (TEAEs) are defined as AEs that started or worsened in severity on or after the first dose of study medication. Laboratory or ECG findings from procedures or samples drawn prior to the first doses of study medication that are assessed/overread after randomization will be considered pre-treatment.

In the case where it is not possible to define an AE as treatment-emergent or not, the AE will be classified by the worst case; i.e. treatment-emergent.

See Appendix 2 for handling of partial dates for AEs.

An overall summary of number of patients within each of the categories described in the subsection below, will be provided as specified in the shells. In addition, the number of patients with each of the following AE events will be presented by SOC and PT and summarized by treatment group and different period (i.e. Treatment period, Follow-up and Overall):

- TEAE
- TEAEs causally related to study medication

- Serious TEAEs
- TEAEs with an outcome of death
- TEAEs leading to discontinuation of blinded study medication
- TEAEs leading to withdrawal from study (TEAEs with a diagnosis of COVID-19, TEAEs with no diagnosis of COVID-19)
- TEAEs by maximum severity

AEs will be identified by using the “Adverse Events” page of the eCRF. Listings will include TEAEs and Non-TEAEs.

Treatment period is defined as the period from the date and time of first dose up to the date and time of last dose.

Follow-up is defined as the period from after the date and time of last dose up to the last date recorded on the study.

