17.2. LABORATORY EVALUATIONS

Results from the central laboratory (or local laboratory where this is required) will be included in the reporting of this study for chemistry, hematology and viral serology. A list of laboratory assessments to be included in the outputs is included in the Appendix 3 of the study protocol. Presentations of all laboratory tests will use standard international (SI) units. However, certain laboratory tests will also be presenting using US units, including liver tests. The handling of re-test and unscheduled measurements is detailed in section 6.4 of the SAP.

The following summaries will be provided for chemistry and hematology data:

- Actual and change from baseline by visit (for quantitative measurements)
- Incidence of abnormal values according to normal range criteria
- Shift from baseline according to normal range criteria (for quantitative measurements and categorical measurements)
- Shift from baseline according to markedly abnormal criteria (for quantitative measurements and categorical measurements)
- Listing of patients meeting markedly abnormal criteria

Viral serology, COVID-19 sample, chemistry and hematology will be listed.

L

FINAL v1.0
 25JUL2022

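### By-visit laboratory, ECG and vital-sign tables carry no on-drug condition, so readings taken after stopping can pull reversible effects slightly towards no difference

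*Protocol*

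**What the plan says.** **The tables.** Protocol 9.4.2 states: "Vital signs and continuous parameters from the ECGs will be summarized by each visit including change from baseline". It treats laboratory data the same way, and it also asks for by-visit counts of vital-sign and ECG values outside preset limits. SAP 17.2, 17.3 and 17.4 request observed values and changes from baseline at each visit. The population is the Safety set (SAP 5.8), which is everyone with at least one full or partial dose. None of these sections mentions time since the last dose.

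**Who may be off drug at a visit.** Under Protocol 7.2, patients who have stopped study medication ideally "will continue to attend scheduled clinic visits and complete important efficacy and safety assessments". Protocol 7.3.1.1 covers patients who stopped before an early-termination visit and have not completed the Week 12 assessments. They may choose to have ECGs at 0 and 1.5 hours, and "These patients will not be dosed with blinded study medication".

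**Where early-termination readings go.** SAP 6.3 states: "Early termination data will be mapped to the next available visit number for by-visit summaries", and refers to SAP 6.4 for the method. SAP 6.4 windows the end-of-study visit for questionnaires, spirometry and rescue use only.

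**Use of data after stopping.** Protocol 9.4.4 brings data collected after treatment withdrawal into the analyses without confining this to efficacy. SAP 7.3 ties the use of off-treatment data to the mITT analyses.

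**Adverse events.** SAP 17.1 does make the distinction: "Treatment period is defined as the period from the date and time of first dose up to the date and time of last dose". Later events are tabulated as follow-up.

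**The concern.** A heart-rate or QTc reading taken weeks after the last dose says little about an effect that disappears when dosing stops. If it counts as an ensifentrine reading at Week 12 or Week 24, it pulls the between-arm difference towards zero. In a safety table that is the unfavourable direction, because an effect looks smaller than it is. An ECG taken 1.5 hours after no dose has the same problem if it is tabulated with ECGs taken 1.5 hours after a dose.

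Stopping can also be linked to what is measured. ECG findings and liver chemistry can each lead to study medication being stopped (Protocol 7.1.2, 7.1.3), and neither by itself requires the patient to leave the study (7.1).

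The SAP conditions on dosing in several other places:

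- Compliance excludes time after treatment withdrawal (15.1).
- The primary endpoint has an analysis limited to readings on randomized treatment (16.1.4).
- Concentrations for a visit are dropped if the two most recent doses were missed, and the sample paired with the 1.5-hour ECG must fall within 0.5 hours of its nominal time after inhalation (20.1).

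The PK sample is therefore tied to dosing, while the ECG taken with it is not. This looks like an omission rather than a choice.

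**Working it through.** **1. The plan's own design figure.** Protocol 9.2 states: "With a 2-sided test at a 5% significance level and 500 vs. 300 evaluable patients in the two groups, there will be an 90% power". The target difference is 59 mL, and the SD "is estimated to be 250 mL". The standard error is 250 × √(1/500 + 1/300) = 18.26 mL. Then 59/18.26 = 3.23, and 3.23 - 1.96 = 1.27, which gives a power of 89.8%. The stated figure is reproduced. This point does not depend on it, because the safety tables are descriptive.

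**2. Dilution of a by-visit mean.** Let f be the share of ensifentrine readings at a visit taken off drug. Assume the effect reverses fully off drug and stopping is unrelated to response. Then

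tabulated difference = (1 - f) × on-drug difference.

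The illustration is 3 bpm. Protocol 2.3 reports this size for peak heart rate against placebo at 6 mg twice daily only, so it is not an estimate for the 3 mg trial dose. The values of f are assumed.

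| f | 3 × (1 - f), bpm |
|---|---|
| 2% | 2.94 |
| 5% | 2.85 |
| 10% | 2.70 |

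**3. Dilution of a by-visit abnormal proportion.** Assume 6% abnormal on drug and 3% on placebo. The ensifentrine column shows 6%(1 - f) + 3%f, which is 5.94%, 5.85% and 5.70% for the same three values of f. The 3-point excess shrinks to 2.94, 2.85 and 2.70 points.

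**4. What determines f.** Let s be the share of ensifentrine patients who stopped drug, and r the share of those who still give a reading off drug. Patients with no reading leave the denominator, so

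f = s·r / (1 - s + s·r).

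| s | r | f | 3 bpm becomes |
|---|---|---|---|
| 10% | 25% | 2.7% | 2.92 |
| 10% | 50% | 5.3% | 2.84 |
| 25% | 10% | 3.2% | 2.90 |
| 25% | 25% | 7.7% | 2.77 |
| 25% | 50% | 14.3% | 2.57 |
| 25% | 100% | 25% | 2.25 |

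Both s and r are assumptions. The 25% borrows the withdrawal rate in Protocol 9.2 as an outer scenario. That rate is study withdrawal, and a patient who has left the study gives no later reading.

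**5. SAP 6.3 against 6.4.** Section 6.3 states a general rule for early-termination data and refers to 6.4 for the method. Section 6.4 names three data types, and laboratory, ECG and vital-sign data are not among them. A programmer could map the early-termination safety readings to a visit or leave them out, and each choice has support in the text. Off-drug readings at scheduled visits do not depend on this step. They carry the nominal visit label and enter the tables either way.

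**The case against.** The strongest case against is that little follows from the silence.

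- **Few off-drug readings.** The three fallback options after stopping (Protocol 7.2.1 to 7.2.3) all omit laboratory tests, ECGs and vital signs. Patients terminating early are asked to stay on medication through that visit if possible. The undosed ECGs are optional and limited to patients without Week 12 assessments. This stands, and it is why f is probably small.
- **Abnormalities are not erased.** A reader might infer that any drug effect is hidden. The documents do not support that. A later normal value cannot remove an on-drug abnormality from a listing or a worst-case table. Unscheduled readings feed worst-case values (SAP 6.3), and patients meeting the markedly abnormal criteria are listed (SAP 17.2 to 17.4). Vital signs are taken pre-dose at every visit (Protocol 8.4.1), so they miss a post-dose peak even on drug.
- **The undosed ECGs may not be in the visit tables.** A reader might take SAP 6.3 as settling that they are. Given SAP 6.4, it does not.
- **An on-drug cut can hide harm.** A reader might conclude that off-drug values should be removed. After a liver stopping criterion is met, Protocol Appendix 9 asks for repeat chemistries within 24 hours or 24 to 72 hours. A short cut-off applied to the shift and markedly-abnormal tables could move those values out of the main tables. This stands against replacing tables, but not against adding them.
- **No test depends on this.** SAP 17 plans no between-group comparisons of safety data, and the table shells (SAP 8) are not among the documents, so they may separate readings by treatment status. Both are fair. But readers take descriptive tables at face value, and the rule belongs in the SAP text.

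**Conclusion.** The point holds in a limited form. Off-drug readings are planned for, the by-visit laboratory, ECG and vital-sign tables have no dosing condition, and adverse events do have one. For reversible effects, by-visit means and by-visit abnormal proportions are pulled towards no difference by (1 - f). With f assumed at 2% to 10%, the loss is 2% to 10% of the effect.

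This rests on full reversal off drug and on stopping being unrelated to response. If patients stop because of the effect, a single factor no longer describes the bias. An on-treatment table would then describe only those still taking drug, which is a reason to show both versions.

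A reader might infer a 25% dilution from Protocol 9.2. The documents do not support it, since that would need a quarter of ensifentrine patients to stop drug and every one of them to return for off-drug readings. No error rate or efficacy conclusion is affected. The change is worth making because it is cheap and removes an ambiguity.

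**What to change.** 1. Keep the all-data tables, including the shift and markedly-abnormal tables, so that delayed abnormalities stay visible.
2. In SAP 17.2 to 17.4, with a matching line in Protocol 9.4.2, add on-treatment by-visit tables for laboratory, ECG and vital-sign data. Define them by a last-dose flag, with the allowed lag stated for each data type before unblinding.
3. Count a 1.5-hour ECG as post-dose only if study medication was given at that visit. Show other such ECGs as off study medication.
4. Reconcile SAP 6.3 with 6.4 by stating whether early-termination laboratory, ECG and vital-sign readings are assigned to a visit and, if so, how.

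Cost: one derived flag, some SAP wording, a few extra descriptive tables, and a slightly smaller n in the on-treatment version. No new data are needed, because dose dates are already used for the adverse-event periods and for exposure (SAP 14).

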9.4.3 Other Analyses

The patient flow including total number of screened patients, number of randomized patients, completers, withdrawn patients (including reason for withdrawal) and patients

included in each of the analysis sets will be summarized by treatment group and for the total.

The number of patients with major protocol deviations will be summarized by category of violation and by treatment group including subset of major protocol deviation leading to exclusion from the per-protocol set.

Demographic and baseline characteristics will be summarized using descriptive statistics for each treatment group and for the total number of randomized patients. Medical history will be coded using MedDRA and summarized by system organ class and preferred term for each treatment group. Prior medications will denote medications used prior to first dose of study drug independent of if stopped at randomization or not. Concomitant medications will denote medications started prior to but continuing after randomization or medications with a start date at or after the randomization date. Prior and concomitant medications will be summarized separately by Anatomical Therapeutic Chemical (ATC) levels 2 and 4.

Compliance to blinded study medication will be computed based on the number of ampules/foil pouch count dispensed and returned. Non-compliance will be defined as a compliance value less than 70% over the full study period. Secondly, compliance will also be computed based on recording of study drug intake in the diary.

The impact of COVID-19 on the study participation of all patients will be captured on a separate eCRF page and include items such as attendance at in-clinic study visits. Details of presentation will be outlined in the Statistical Analysis Plan.

9.4.4 Missing Data

All data collected after treatment withdrawal will be used in the analyses. Patients withdrawn from study will perform an End-of-Study visit after decision to withdraw the patient has been made. Data collected at such visits will be used for analysis even if outside the visit window for the endpoint. Remaining missing data will primarily be imputed using multiple imputation based on baseline characteristics and data collected at post-randomization visits. In addition, a worst-case scenario using the average change in the opposite treatment group will be used for imputation as a sensitivity analysis. For the responder analysis of SGRQ, patients with no available data for imputation will be considered non-responders as a sensitivity analysis. In exacerbation analyses, patients are included with data collected up to last day in the treatment period/period of recording following treatment withdrawal.

9.4.5 Pharmacokinetics

All reported plasma concentrations will be listed and summarized using appropriate descriptive statistics. Graphical presentations of concentration data will be provided, if appropriate.

Ensifentrine concentrations will be used for a population PK analysis of ensifentrine. The pharmacokinetics of ensifentrine will be characterized by nonlinear mixed effects modeling based on sparse sampling. From the established model, the influence of various demographic covariates (eg, body weight, gender, genotype) and other patient-specific factors on ensifentrine exposure may be assessed. The data from this study may be combined with data collected from other studies for a pooled meta-analysis using modeling and simulation to estimate PK parameters as well as exposure – response (safety) correlations. The population PK (and population PK-PD, if performed) analyses will be performed in accordance with a separate modeling data analysis plan and will be reported outside of the clinical study report.

9.5 Interim Analyses

There will be no formal interim analysis in the study. Blinded data will be monitored continuously and the assumptions for the variability in data checked as well as the withdrawal rate.

11.0 APPENDICES

11.1 Appendix 1: Abbreviations

| | |
|------------------|---|
| AE | Adverse event |
| ALT | Alanine aminotransferase |
| ANCOVA | Analysis of covariance |
| Anti-HBc | Hepatitis B core antibody |
| Anti-HBs | Hepatitis B surface antibody |
| AST | Aspartate aminotransferase |
| ATC | Anatomical Therapeutic Chemical Classification System |
| ATS | American Thoracic Society |
| AUC | Area under the curve |
| AV | Atrioventricular |
| BDI | Baseline dyspnea index |
| BID | Twice daily |
| bmp | Beats per minute |
| CFR | Code of Federal Regulations |
| BMI | Body mass index |
| CI | Confidence interval |
| COPD | Chronic obstructive pulmonary disease |
| COVID-19 | Coronavirus disease 2019 |
| CSR | Clinical Study Report |
| CRP | C-reactive protein |
| CXR | Chest X-ray |
| CT | Computed tomography |
| CV | Coefficient of variation |
| DBL | Data Base Lock |
| DNA | Deoxyribonucleic acid |
| ECG | Electrocardiogram |
| eCRF | Electronic case report form |
| e-Diary | Electronic diary |
| EQ-5D-5L | EuroQol-5-Domain Questionnaire |
| E-RS | Evaluating Respiratory Symptoms |
| ERS | European Respiratory Society |
| ERT | eResearch Technology |
| FAS | Full Analysis Set |
| FEV ₁ | Forced expiratory volume in 1 second |

| | |
|--------|--|
| FSH | Follicle stimulating hormone |
| FVC | Forced vital capacity |
| GCP | Good Clinical Practice |
| GOLD | Global Initiative for Chronic Obstructive Lung Disease |
| HBsAg | Hepatitis B surface antigen |
| HCV | Hepatitis C virus |
| HIV | Human immunodeficiency virus |
| HRT | Hormonal replacement therapy |
| HRU | Healthcare resource utilization |
| IB | Investigator's brochure |
| IC | Inspiratory capacity |
| ICF | Informed consent form |
| ICH | International Council for Harmonisation |
| ICS | Inhaled corticosteroid(s) |
| IEC | Independent Ethics Committee |
| IgM | Immunoglobulin M |
| IL | Interleukin |
| INR | International normalized ratio |
| INN | International Non-proprietary Name |
| IRB | Institutional Review Board |
| IRT | Interactive Response Technology |
| IT | Information technology |
| LABA | Long-acting β 2-agonist |
| LAHB | Left anterior hemiblock |
| LAMA | Long-acting muscarinic antagonist |
| LDPE | Low density polyethylene |
| LPHB | Left posterior hemiblock |
| LOCF | Last observation carried forward |
| LS | Least square |
| MAD | Multiple ascending dose(s) |
| MCID | Minimum clinically important difference |
| MedDRA | Medical Dictionary for Regulatory Activities |
| mITT | Modified Intent-to-Treat |
| mMRC | Modified Medical Research Council |
| MMRM | Mixed model for repeated measures |
| NYH | New York Health |

| | |
|-------|---|
| PDE | Phosphodiesterase |
| PCR | Polymerase Chain Reaction |
| PGAC | Patient Global Assessment of Change |
| PK | Pharmacokinetic(s) |
| PP | Per-protocol |
| PT | Preferred term |
| QoL | Quality of life |
| QTcF | QT interval corrected for heart rate using Fridericia's formula |
| QTL | Quality tolerance limit |
| RBBB | Right bundle branch block |
| RNA | Ribonucleic Acid |
| SABA | Short-acting β 2 agonists |
| SAE | Serious adverse event |
| SAMA | Short-acting muscarinic antagonists |
| SAP | Statistical analysis plan |
| SD | Standard deviation |
| SOA | Schedule of Activities |
| SOC | System organ class |
| SGRQ | St George's Respiratory Questionnaire |
| SUSAR | Suspected unexpected serious adverse reaction |
| TDI | Transition Dyspnea Index |
| TEAE | Treatment-emergent adverse event |
| UK | United Kingdom |
| ULN | Upper limit of normal |
| USA | United States of America |
| WOCBP | Women of Childbearing Potential |

DEFINITION OF TERMS

| | |
|-------------|--|
| QT interval | The portion of an electrocardiogram between the onset of the Q wave and the end of the T wave. |
|-------------|--|

